The co-primary endpoints of this study are safety, tolerability and feasibility in cohort 1, followed by safety and feasibility in cohort 2. Safety will be monitored through the rate of all treated patients that develop adverse events (including serious and non-serious, as well as adverse events of special importance AESIs) and dose-limiting toxicities from commencement of durvalumab/RT or durvalumab/tremelimumab/RT until 30 days postoperatively or 100 days after the last dose of immunotherapy whichever is longer, or any pre-defined pulmonary DLTs that occur from the date of surgery until 30 days postoperatively. The DLT observation window will be defined as the time from the date of commencement of immunotherapy until 30 days post-surgery or 100 days after last immunotherapy dose, whichever is longer. Safety will be monitored continuously for all patients. A Bayesian safety monitoring rule will be used to evaluate the rate of adverse events of interest continuously, from the 3rd evaluable patient, and accrual will be suspended at any time if there is sufficient evidence of excessive toxicity. Specifically, the Bayesian toxicity monitoring rule suspends accrual anytime if the posterior probability of adverse event of interest being larger than 25%, is 70% or higher. The following table gives the corresponding stopping rule for the 16 evaluable patients:

#Patients with DLT	2	3	4	5	6
Out of total #patients treated	3-4	5-7	8-11	12-13	16

Feasibility will be monitored through the proportion of patients who undergo surgery within the planned surgical window: 6-8 weeks after completion of thoracic RT. We will use a probability-based decision rule to decide if the probability of successfully proceeding to surgery as planned is convincingly less than 75%. A Bayesian monitoring rule would apply and suspend the accrual if there is at least 90% probability that less than 75% of patients can continue to surgery without treatment-related delays, as shown in the following table:

#Patients planned for surgical resection	1	2	3	5	6	7	8
resection							
Out of total # evaluable patients	6	7	8-9	10	13	14-15	16

Exploratory analyses as detailed in the biomarker table/summary will be presented descriptively, and are detailed in the researcher comments section.

Sample Size Determination:

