Scheduling Window (Days):	-28 to -1	±3	± 3		± 3	Within 7 days of planned surgery	Within 72 hours of planned surgery		30 days post- Surgery** (± 3)	100 days post- Surgery** (± 7)
Week	-4 to -1	1		4	8	11-15	11-15		4 weeks post Surgery	3 months post surgery
Urinalysis	Х									
Pulmonary Function Tests (including FEV1, FVC, DLCO)	X ⁹									
Radiologic Assessments										
PET/CT with contrast ⁶	X*					X*				
MRI Brain with contrast	X^{10}									
CT chest/abdomen/pelvis with contrast with recist read ⁶	X*					X*				
Correlative Analyses										
Pre-treatment Tissue Collection ⁷	Х									
Blood collection	Х	Х	Х		Χ		Х		Х	Х
Post-treatment Tissue ⁷								Х		

NOTE: In order to minimize the need for research-only in-person visits, telemedicine visits may be substituted for in-person clinical trial visits or portions of clinical trial visits where determined to be appropriate and where determined by the investigator not to increase the participants risks. Prior to initiating telemedicine for study visits the study team will explain to the participant, what a telemedicine visit entails and confirm that the study participant is in agreement and able to proceed with this method. Telemedicine acknowledgement will be obtained in accordance with the Guidance for Use of Telemedicine in Research. In the event telemedicine is not deemed feasible, the study visit will proceed as an in-person visit. Telemedicine visits will be conducted using HIPAA compliant method approved by the Health System and within licensing restrictions.

- At the beginning of the infusion (at 0 minutes), At 30 minutes during the infusion (±5 minutes), At the end of the infusion (at 60 minutes ±5 minutes)
- In the 1 hour observation period post-infusion: 30 and 60 minutes after the infusion (i.e., 90 and 120 minutes from the start of the infusion) (±5 minutes) for the first infusion only and then for subsequent infusions as clinically indicated. If the infusion takes longer than 60 minutes, then blood pressure and pulse measurements should follow the principles as described above or more frequently if clinically indicated.

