^{*} All assessments to be performed pre-infusion unless stated otherwise ** If patients do not proceed to surgery, they will proceed to the safety follow-up visit at a time point 100 days after commencement of immunotherapy. ¹Subjects will have their blood pressure and pulse measured before, during, and after the infusion at the following times (based on a 60-minute infusion):

²EKG during screening and at Day1 – baseline. Thereafter as clinically indicated. Baseline and abnormal EKG at any time in triplicate others single.

³ If screening laboratory assessments are performed within 3 days prior to Day 1 they do not need to be repeated at Day 1. Results for safety bloods must be available and reviewed before commencing an infusion. Gamma glutamyltransferase tested at Screening, Day 1 and as clinically indicated.

⁴ Pre-menopausal female subjects of childbearing potential only. If urine test is positive or not evaluable, serum test is required

⁵ Free T3 and free T4 will only be measured if TSH is abnormal. They should also be measured if there is clinical suspicion of an adverse event related to the endocrine system.

⁶CT of the Chest/Abdomen/Pelvis is required between days -1 to days -28. A PET/CT may be substituted for a CT Chest/Abdomen/Pelvis if it done within 3 months prior to Cycle 1 Day 1. Either a PET/CT or CT of the Chest/Abdomen/Pelvis may be used for Preoperative imaging within 3 weeks of planned surgical resection date.

⁷Pre-treatment and post-treatment tissue will be collected as in section 8.

⁸Blood collection for correlative analysis will be taken at 12 month time point only during follow-up

⁹Assessment of lung function can be done within 3 months of treatment start as it is considered standard of care in the staging evaluation of patients with resectable NSCLC

¹⁰ MRI Brain imaging within 3 months of treatment start as it is considered standard of care in the staging evaluation of patients with NSCLC

LONG TERM FOLLOW UP

Evaluation	Time Since Last Dose of MEDI4736 for those who did not proceed to surgery per SOC For those who did proceed to surgery, LT follow up would be scheduled from surgery date following SOC Months (±2 weeks) Long term follow up visits can be done via telehealth						Every 12 weeks (+/- 2 weeks) or per SOC for years 2 and 3	
	4	6	8	9	10	12		
Physical examination ^a		Х		Х		Х		
Vital signs (temperature, respiratory rate, blood pressure, pulse)		X		X		х		
Weight		X		Х		Х		
AE/SAE assessment		х		Х		X	Х	

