3.1.5. Toxicity assessments

Safety will be monitored continuously by the study investigators for patients in both cohort 1 and cohort 2 through day 90 following the last dose of study therapy or 30 days after the day of surgery, whichever happens later. Details of safety assessments as detailed in

section 9.0 of this protocol. A detailed statistical analysis plan for safety and feasibility is contained in section 11 of this protocol.

Dose Delays due to Toxicity:

If patients, after receiving the first dose of study therapy (Day 1) are unable to receive the second dose on Day 30 (+/-3 days), therapy may be deferred as long as the second dose is received during the time period of thoracic radiation. If this is not possible, they will be discontinued from study therapy and will proceed to surgery after standard preoperative evaluation.

If patients, after receiving the second dose of study therapy (Day 30) are unable to receive the

third dose on Day 60 (+/-3 days), therapy may be deferred as long as the third dose is received during the pre-surgical window prior to planned surgery. If this is not possible, they will be discontinued from study therapy and will proceed to surgery after standard preoperative evaluation. Prior to surgery any treatment-related toxicity should have resolved to ≤grade 1. □

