6.2. Dosage and Administration

6.2.1. Durvalumab monotherapy or Durvalumab and Tremelimumab

Dosage of study therapy to be administered in this protocol is outlined below in Table 2.

In cohort 1: Three doses of durvalumab monotherapy will be administered to enrolled patients on Days 1, 30 and 60 (+/- 3 days) concurrently with standard thoracic radiation from day 1 until days 25-28, prior to planned surgery. Thoracic surgery will take place 6-8 weeks after completion of thoracic radiation.

In cohort 2: Three doses of durvalumab + tremelimumab will be administered to enrolled patients on Days 1, 30 and 60 (+/- 3 days) concurrently with standard thoracic radiation from day 1 until day 25-28 prior to planned surgery. Thoracic surgery will take place 6-8 weeks after completion of thoracic radiation.

Dosing of study therapy is flat dosing.

TABLE 2: TRIAL TREATMENT

Drug	Dose/Potency*	Dose Frequency	Route of Administration	Regimen/Treatment Period	Use
Durvalumab	1500 mg	Q4W	IV infusion	Day 1 of each 4 week cycle	Experimental
Tremelimumab	75mg	Q4W	IV infusion	Day 1 of each 4 week cycle	Experimental
(cohort 2 only)					

18 Nov 2020 Page **73** of **164**

The rationale for dosing is outlined in sections 1.0 and 5.0. Trial treatment should begin on the day of registration or as close as possible to the date on which treatment is allocated/assigned. Refer to Section 5.0 for the administration and monitoring of administration of durvalumab and tremelimumab.

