6.3. Definition of Dose Limiting Toxicity (DLT)

Dose-limiting toxicities (DLTs) will be evaluated from the first day of administration of durvalumab (cohort 1) or durvalumab+tremelimumab (cohort 2), in this trial. The period for evaluating DLTs will be from the day of first administration of study therapy until 30 days after surgical resection or 100 days following the last dose of study therapy, whichever occurs later. Subjects who do not remain on the study up to this time for reasons other than DLT will be replaced with another subject. Grading of DLTs will follow the guidelines provided in the Common Terminology Criteria for Adverse Events (CTCAE) version 4.0. A patient who experiences a DLT will be permanently discontinued from treatment and will proceed to surgery after standard preoperative evaluation by a surgeon and anesthesiologist. Prior to surgery any treatment related toxicity should have resolved to ≤grade 1. [5]

A DLT will be defined as any Grade 3 or higher toxicity that occurs during the DLT evaluation period. Toxicity that is clearly and directly related to the primary disease or to another etiology is excluded from this definition. The following will be DLTs:

- Any Grade 4 irAE
- Any ≥ Grade 3 colitis
- Any Grade 3 or 4 non-infectious pneumonitis irrespective of duration
- Any Grade 2 pneumonitis that does not resolve to ≤ Grade 1 within 3 days of the initiation of maximal supportive care
- Any Grade 3 irAE, excluding colitis or pneumonitis, that does not downgrade to Grade 2 within 3
 days after onset of the event despite optimal medical management including systemic
 corticosteroids or does not downgrade to ≤ Grade 1 or baseline within 14 days
- Liver transaminase elevation > 8 × ULN or total bilirubin > 5 × ULN
- Any ≥ Grade 3 non-irAE, except for the exclusions listed below

The definition excludes the following conditions:

- Grade 3 fatigue lasting ≤ 7 days
- Grade 3 endocrine disorder (thyroid, pituitary, and/or adrenal insufficiency) that is managed
 with or without systemic corticosteroid therapy and/or hormone replacement therapy and the
 subject is asymptomatic
- Grade 3 inflammatory reaction attributed to a local antitumor response (e.g., inflammatory reaction at sites of metastatic disease, lymph nodes, etc.)
- Concurrent vitiligo or alopecia of any AE grade
- Grade 3 infusion-related reaction (first occurrence and in the absence of steroid prophylaxis) that resolves within 6 hours with appropriate clinical management

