12.2. Study Endpoints Definition

12.2.1. Primary Endpoints

Safety of durvalumab monothererapy (cohort 1) +/- durvalumab+tremelimumab (cohort 2) administered preoperatively together with thoracic radiation in stage III NSCLC.

Safety will be measured by the frequency of any of the following events:

• Drug-related adverse events occurring up to 100 days after the last dose of immunotherapy or 30 days after surgery (whichever is longer).

18-Nov-2020 Page **114** of **164**

- Serious adverse events occurring up to 100 days after the last dose of immunotherapy or 30 days after surgery (whichever is longer).
- Clinical laboratory test by worst toxicity grade (as assessed at the time intervals outlined in the Schedule of Assessments, Figure 1.)

Feasibility of preoperative administration of durvalumab monothererapy (cohort 1) +/- durvalumab+tremelimumab (cohort 2) concurrently with thoracic radiation in stage III NSCLC

Feasibility will be evaluated through the proportion of evaluable patients who successfully complete preoperative treatment and proceed to surgery without any extended treatment-related delays defined as >8 weeks from the last day of thoracic radiation.

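### For patients who do not proceed to surgery, the safety visit is timed from the first dose and falls about 60 days before the DLT window closes after three on-schedule doses

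*Combined protocol and SAP*

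**What the plan says.** **The visit.** In Figure 1 the safety follow-up columns are set 30 and 100 days after surgery. The ** footnote covers patients who are not operated on: "they will proceed to the safety follow-up visit at a time point 100 days after commencement of immunotherapy".

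**The window.** Section 6.3 evaluates DLTs from the first administration "until 30 days after surgical resection or 100 days following the last dose of study therapy, whichever occurs later". Section 12.2.1 uses the same end point for drug-related and serious adverse events, and the synopsis agrees. Without surgery, the end point is 100 days after the last dose.

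**The doses.** Section 6.2.1 gives doses on days 1, 30 and 60, each ±3 days. Section 3.1.5 allows a late third dose: "therapy may be deferred as long as the third dose is received during the pre-surgical window prior to planned surgery".

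**Its role.** The synopsis states: "The co-primary endpoints of this study are safety, tolerability and feasibility in cohort 1". Section 12.1 defines an evaluable patient by at least one dose and complete toxicity follow-up; surgery is not required.

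**Other observation.**
- Section 3.1.6.2 has records reviewed weekly to 100 days after the last dose, or 30 days after surgery if later.
- Section 9.3.1 records AEs from consent through follow-up.
- The synopsis and 8.1.4 describe 12-weekly follow-up in the first year after therapy. The synopsis adds laboratory tests and AE assessment.
- The Long Term Follow Up table counts from the last dose for non-operated patients. It marks AE assessment at months 6, 9 and 12, marks only subsequent therapy and survival status at month 4, and leaves the hematology and thyroid rows blank.

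**The concern.** The footnote and the window start from different dates. For anyone given more than one dose, the visit comes before the end of the period over which the co-primary safety endpoint is counted.

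Laboratory toxicity is the most exposed. Section 12.2.1 takes worst laboratory grade from the Figure 1 time points. Section 9.3.5 reports deterioration in protocol-mandated laboratory values as an AE only if it is serious or leads to discontinuation. Section 6.3 counts transaminases above 8 × ULN as a DLT. After dosing has ended, an asymptomatic rise of that kind is found only if a sample is drawn.

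Any loss would lower the DLT count that feeds the stopping rule in 12.2.2 and the decision to open cohort 2. It would arise in patients who did not reach surgery, a group that may include some with toxicity or progression.

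**Working it through.** The plan gives no figure for this gap, so it is derived from the plan's own dates.

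**Inputs**
- Dose days 1, 30 and 60, ±3 (6.2.1, Figure 1).
- Visit without surgery: first dose + 100 days (Figure 1, footnote **). This is day 101, or day 100 if the first dosing day is counted as one.
- Window end without surgery: last dose + 100 days (6.3).
- Visit tolerance ±7 days. Figure 1 gives it for the visit 100 days after surgery; carrying it over to the footnote visit is an assumption.
- Surgery 42 to 56 days after radiation ends (6.2.1). Radiation ends by day 28 in 6.2.1; 25 fractions at five a week (6.2.2.3) take until about day 33 to 35.

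**Gap = (last dose day + 100) − visit day**

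| Doses given | Window closes | Gap |
|---|---|---|
| 3 | 60 + 100 = 160 | 59 to 60 days |
| 2 | 30 + 100 = 130 | 29 to 30 days |
| 1 | 1 + 100 = 101 | 0 to 1 day |

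- With tolerances after three doses, the gap runs from (57 + 100) − (101 + 7) = 49 days to (63 + 100) − (101 − 7) = 69 days.
- If dose 3 is deferred to the last day of the surgical window (an outer case), it falls on day 28 + 56 = 84 or 35 + 56 = 91. The gap is then 184 − 101 = 83 or 191 − 101 = 90 days.
- Under the 90-day wording used elsewhere, the window closes on day 60 + 90 = 150, a gap of 49 to 50 days. That wording also counts from the last dose.

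**What is scheduled between the visit and day 160 (three doses)**
- Long Term table, month 4: about day 182 (168 to 196 with ±2 weeks). This is after the window and has no AE review.
- Long Term table, month 6, the first AE assessment: about day 243 (229 to 257).
- 12-weekly text, counted from the last dose: 60 + 84 = day 144 (137 to 151), 16 days before the window closes. After two doses it is 30 + 84 = day 114, also 16 days before.
- Operated patients, for comparison: surgery falls on day 33 + 42 = 75 to 35 + 56 = 91. Safety visits follow on days 105 to 121 and 175 to 191. Their window also closes on day 160, because surgery + 30 comes earlier.

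**Possible effect on the stopping rule.** Table 10.2 is the nearest stated figure that depends on full DLT ascertainment. I used the Beta(0.05, 0.95) prior and suspended when the posterior probability of a rate above 25% is at least 70%. The boundaries are 2 of 3–4, 3 of 5–7, 4 of 8–11, 5 of 12–14 and 6 of 15–16. An exact recursion to 16 patients gives:

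| True risk | 0.15 | 0.20 | 0.25 | 0.30 | 0.35 |
|---|---|---|---|---|---|
| Table 10.2 | 15.8% | 29.3% | 43.1% | 60% | 72.8% |
| Recomputed | 16.3% | 29.3% | 44.3% | 59.4% | 72.8% |

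The table is reproduced to within 1.2 points.

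As illustration only, suppose a share f of patients is not operated on, a share m of their DLTs is missed, and their DLT risk equals that of the others. The observed rate is then p(1 − fm). At p = 0.25:
- f = 0.10, m = 0.10 gives 0.2475, and stopping falls from 44.3% to 43.5%.
- f = 0.25, m = 0.50 gives 0.219, and stopping falls to 34.8%.

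Neither f nor m is in the documents. In a cohort of 16, one missed DLT moves the reported rate by 1/16 = 6.25 points. Under Table 10.1, 4 of 11 suspends accrual and 3 of 11 does not.

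**The case against.** The strongest reply is that observation does not end at the footnote visit.

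- **12-weekly follow-up.** If counted from the last dose, it puts a visit near day 144 and leaves about 16 days uncovered instead of 60. This stands as a reading of the synopsis and 8.1.4. However, 8.1.4 refers to the Schedule of Assessments for its procedures, and the Long Term table there shows no such visit. The texts conflict, and a site cannot tell which applies.
- **Record review and AE recording.** Both continue through the window, with contact with outside physicians if care moves. Symptomatic severe pneumonitis or hepatitis would probably be captured. Record review orders no sample, so the point about laboratory events remains.
- **Operated patients.** They too have no Figure 1 visit between about day 121 and day 160. The difference is that their last visit follows the end of the window and can look back over it.
- **Who is affected.** Patients with an earlier DLT are already counted. Several groups are replaced: those with incomplete radiation, those suitable only for pneumonectomy, and those who leave before the DLT period ends for reasons other than DLT. The number of non-operated patients entering the DLT denominator is therefore unknown.

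A reader might infer that nothing at all is scheduled before month 6, or that a site will treat the day-100 visit as the end of toxicity follow-up. The first is true only of Figure 1 and the Long Term table. The second is not stated anywhere: 8.1.3 sends early discontinuers to the follow-up phase after the safety visit, but 6.3 defines the DLT period explicitly.

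**Conclusion.** The contradiction is real. The footnote counts from the first dose, and every statement of the safety window without surgery counts from the last. After three on-schedule doses the visit precedes the end of the window by about 60 days nominally, and after two by about 30; after one there is essentially no gap. Sixty days is not a maximum, because tolerances or a deferred third dose lengthen it.

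Neither Figure 1 nor the Long Term table gives these patients a visit or laboratory sample at or near the end of the window. Asymptomatic laboratory DLTs are the most exposed.

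It would go too far to conclude that co-primary safety is biased downwards by a known amount, or that these patients go unobserved. The direction of any loss is clear, but its size depends on how many patients are not operated on and how many of their DLTs arise late and silently. The documents give neither, so the stopping probabilities above are not estimates. Because the endpoint is co-primary and the remedy is small, the passages should be reconciled.

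**What to change.** 1. Amend the ** footnote so that the final safety visit of non-operated patients, with AE review and safety laboratory tests, is timed from the last dose and does not precede the end of the DLT window. On the 100-day window in 6.3, this is nominally day 160 after three doses, 130 after two and 101 after one. Set the visit tolerance so that the visit cannot fall early.
2. Reconcile that visit with the 12-weekly follow-up in the synopsis and 8.1.4 and with the Long Term Follow Up table. Moving the visit alone would remove the one now set about 40 days after dose 3, so the amended schedule should keep an interim observation.
3. Reconcile the window itself: 3.1.5, 12.1 and 12.2.2 use 90 days, and 10.1.1 and 14.2 use 90 days or 30 days after surgery, whichever comes first.
4. In 12.1, count a patient without a DLT as having complete toxicity follow-up only once the reconciled window has closed.

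The cost is one amendment to a footnote and the matching follow-up text. The safety visit is re-timed. If the 12-weekly visit in the synopsis serves as the interim observation, nothing is added beyond what the synopsis already describes; if the day-100 visit is kept as well, the cost is one extra visit per non-operated patient.

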1.1. Disease Background

Immune responses directed against tumors are one of the body's natural defence against the growth and proliferation of cancer cells. However, over time and under pressure from immune attack, cancers develop strategies to evade immune-mediated killing allowing them to develop unchecked. One such mechanism involves upregulation of surface proteins that deliver inhibitory signals to cytotoxic T cells. Programmed cell death ligand 1 (PD-L1) is one such protein, and is upregulated in a broad range of cancers with a high frequency, with up to 88% expression in some tumor types. In a number of these cancers, including lung¹, renal²; pancreatic³; ovarian cancer⁴, and hematologic malignancies^{5, 6} tumor cell expression of PD-L1 is associated with reduced survival and an unfavorable prognosis.

Programmed cell death ligand 1 is part of a complex system of receptors and ligands that are involved in controlling T-cell activation. PD-L1 acts at multiple sites in the body to help regulate normal immune responses and is utilized by tumors to help evade detection and elimination by the host immune system tumor response. In the lymph nodes, PD-L1 on antigen-presenting cells binds to PD-1 or CD80 on activated T cells and delivers an inhibitory signal to the T cell⁷. This results in reduced T-cell activation and fewer activated T cells in circulation. In the tumor microenvironment, PD-L1 expressed on tumor cells binds to PD-1 and CD80 on activated T cells reaching the tumor. This delivers an inhibitory signal to those T cells, preventing them from killing target cancer cells and protecting the tumor from immune elimination⁸.

Immune responses directed against tumors are one of the body's natural defenses against the growth and proliferation of cancer cells. T cells play a critical role in antitumor immunity and their infiltration and activity have been linked to improved prognosis in a number of cancers⁹⁻¹¹. Immune evasion, primarily through suppression of T-cell activity, is now recognized as one of the hallmarks of cancer. Such evasion can occur via a range of mechanisms including production of suppressive cytokines such as IL-10, secretion of chemokines and growth factors that recruit and sustain suppressive regulatory T cells (Tregs) and inflammatory macrophages, and expression of inhibitory surface molecules such as B7-H1. Tumor types characterized as being responsive to immunotherapy-based approaches include melanoma^{12, 13}, renal cell carcinoma¹⁴, bladder cancer¹⁵, and malignant mesothelioma¹⁶. Inhibition of CTLA-4 signaling is a validated approach to cancer therapy, as shown by the approval in 2011 of ipilimumab for the treatment of metastatic melanoma based on statistically significant and clinically meaningful improvement in OS¹².

In general, tumor response rates to anti-CTLA-4 therapy are low (~10%). However, in patients who respond, the responses are generally durable, lasting several months even in patients with aggressive tumors such as refractory metastatic melanoma. Because these agents work through activation of the immune system and not by directly targeting the tumor, responses can occur late and some patients may have perceived progression of their disease in advance of developing disease stabilization or a tumor response. In some cases, early growth of pre-existing

18 Nov 2020 Page **38** of **164**

lesions or the appearance of new lesions may have been due to immune-cell infiltration into the tumor and not due to proliferation and extension of neoplastic cells, per se¹⁷. Overall, although the impact on conventionally-defined PFS can be small, durable response or stable disease seen in a proportion of patients can lead to significant prolongation of OS. The melanoma data with ipilimumab clearly demonstrate that a small proportion of patients with an objective response had significant prolongation of OS, supporting the development of this class of agents in other tumors. Although Phase 2 and Phase 3 studies of tremelimumab in metastatic melanoma did not meet the primary endpoints of response rate and OS, respectively, the data suggest activity of tremelimumab in melanoma^{18, 19}. In a large Phase 3 randomized study comparing tremelimumab with dacarbazine (DTIC)/temozolomide in patients with advanced melanoma, the reported median OS in the final analysis was 12.58 months for tremelimumab versus 10.71 months for DTIC/temozolomide (HR = 1.1416, p = 0.1272)¹⁹.

